3. STUDY DESIGN

The pilot phase is a double-blind, placebo-controlled randomized component designed to document safety and efficacy endpoint assessments and to determine the feasibility of recruitment and enrollment of symptomatic, community dwelling, adult, outpatients with COVID-19 as well as patient compliance with the protocol.

The pilot phase will enroll a total of 60 participants (30 in each arm). Participants will be followed for 14 days on treatment with an additional 10 weeks off treatment. Participants who do not start study treatment will be replaced. Participants will be randomized 1:1 as individuals. Participants will receive either XFBD (10 g orally twice a day) for 14 days or a placebo twice a day for 14 days.

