6. CLINICAL AND LABORATORY EVALUATIONS

6.1 Schedule of Evaluations (SOE)

Table 6.1

Evaluations	Screening ^a	Entry	Post Entry Evaluation									Premature Study Discontinuation		
			Day 0	Day 1	Day 3	Day 7	Day 14	Day 21	Day 28	Day 42	Week 12			
Visit Location			Remote											
Informed Consent	X													
Documentation of Positive SARS-CoV-2 Molecular Test	X													
COVID-19 Symptom Screen	X													
Medical/Medication History Form	X													
Identify health care providers	X													
Identify Secondary Contacts ^b	X													
Study Kit Dispensed ^c		X												
Self-administration of Study Agent PO BID		X	X	X	X	X								
Confirmation of First Dose		X												
Distribution of Symptom Self Reporting Application		X												
Daily study questions via study App or phone			X	X	X	X	X					X		
Adverse Events Tracking					X	X	X	X	X					
Review of Adherence				X	X	X						X		
At home specimen collection for SARS-CoV-2 viral RNA testing			X		X	X								
Study Endpoint Determination			X	X	X	X	X	X	X	X ^d		X		

^a Participants must begin study treatment within 96 hours of onset of their first symptom. ^b To enable updating data in the event the participant is hospitalized or dies. ^c Study kit contains: Copy of informed consent, Information about the study, Instructions on study procedures, QR Code and Internet link for Symptom Self Reporting Application, Study agent, Instructions on what to do if they have worsening symptoms/become hospitalized ^d Direct contact and medical record review.

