6.2.8 Study Kit Dispensed

The kit will include:

- 6.1.1.1 Study agent
- 6.1.1.2 Blank copy of informed consent and HIPPA authorization
- 6.1.1.3 Information about the study
- 6.1.1.4 Instructions on study procedures
- 6.1.1.5 3 sets of COVID-19 Test Home Collections Kits ^a
- 6.1.1.6 QR Code and Internet link for Symptom Self Reporting Application (Appendix VI)
- 6.1.1.7 Instructions on what to do if they have worsening symptoms/become hospitalized

^aAn FDA Emergency Use Authorization approved home kit solution such as the Fulgent COVID-19 by RT-PCR test will be used. (73) It is a nasal swab collection followed by a FDA EUA approved PCR test conducted in the CLIA/CAP laboratory of Fulgent Genomics, determining the presence or absence of RNA from SARS-CoV-2 virus. The kit will include instructions, a swab and tube, alcohol prep pad, kit ID stickers, biohazard bag, absorbent sheet, return label, return box, and return envelope. The participant will be provided sample collection instructions and how to return the sample both in an illustrated print out and video. (74) The print outs are available in the supplemental materials.

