6.2.9 Study Day 1 (day of first study substance administration) – Remote

Study staff will confirm the first dose taken by the participant by telephone. Participants who refuse the first dose after 2 days will be discontinued from the study.

Study staff will also confirm by telephone the completion of first nasal swab home kit to be mailed out within 24 hours. The nasal swab home kit can be completed within days 1 to 3 to accommodate shipping limitations.

The participant will utilize an application (app) available to self-report symptoms once daily as Patient-reported outcomes (PRO). The application clarifies to the study participant the information they are providing is not a substitute for standard COVID-19 care with their health care provider. The participant's completion of the self-report or PRO will be reviewed. If the participant does not complete their self-report, study staff will initiate contact to facilitate the completion of the daily self-report PRO. If the self-report or PRO discloses onset or worsening of the symptom of shortness of breath or worsening of other symptoms the participant will be instructed to call 911, telephone their health care provider or go to the health care provider urgent or emergency care facility.

Study staff will obtain and review the participant's EHR for pertinent information for the primary, secondary and exploratory endpoints.

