10.2.2 Secondary Outcome Measures

- 10.2.2.1 To document the effect of XFBD on Symptom Severity Score within 28 days of

study entry.

- 10.2.2.2 To document the proportion of patients who are compliant taking greater than 90% of the test substance as measured by self-report
- 10.2.2.3 To document the proportion of patients who comply with symptom monitoring.
- 10.2.2.4 To document the proportion of patients who comply with repeated clinical testing.
- 10.2.2.5 To document cumulative incidence of serious adverse events, and adverse events leading to early discontinuation of XFBD or placebo.
- 10.2.2.6 To document cumulative incidence of grade 3 and 4 adverse events.
- 10.2.2.7 To obtain levels (detectable versus not detectable, and continuous on log10 scale) of SARS-CoV-2 RNA from nasal swabs at approximately days 1, 7 and 14 among a subset.

10.3 *Randomization and Stratification*

[figure not shown]
Eligible participants will be randomized using a 1:1 ratio to each of the study arms. Housemates of participants previously enrolled will be independently randomized so that housemates will not be clustered within treatment group.

Randomization will be stratified by “high” vs “low” risk of severe disease, where “high” risk is defined by any of the following: age ≥ 60 years, or having any of a number of conditions, as described in section 3.3.

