10.6.2 Secondary Outcomes

Symptom severity scores will be determined from the COVID-19 symptom PROs reported daily by participants. Each symptom is rated by the participant on a scale from 0-4. Although the seriousness of the symptoms are not equal, summing the individual symptom ratings will give a rough measure of the participant's disease severity. These daily symptom severity scores will be summed over the 28-day period using area under the curve (AUC). Comparisons of this AUC, as well as weekly symptom severity scores, by age, race/ethnicity, gender, risk group and assigned treatment will be performed using Wilcoxon rank sum tests. For this, and all comparisons by demographic or treatment variables, the results will be considered for planning purposes only. Secondary outcomes 2, 3, and 4 involve compliance proportions and will be documented in total and compared by demographic and treatment variables using Fisher exact tests. Secondary outcomes 5, 6, and 7 involve event rates which will be calculated in total and compared by demographic and treatment variables using negative binomial regression. Detectable versus not detectable SARS-CoV-2 RNA from nasal swabs at days 7 and 14 will be compared by demographic and treatment variables using Fisher exact tests, and continuous measures of SARS-CoV-2 RNA (on log10 scale) will be assessed for normality and tested using t-tests or Wilcoxon rank sum tests, as appropriate.

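### Log10 SARS-CoV-2 RNA is tested with no stated baseline or stratum adjustment, and the Day 1 swab is not guaranteed to precede the first dose

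*Combined protocol and SAP*

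**What the plan says.** Objective 1.3.8 and outcome 10.2.2.7 both call for "SARS-CoV-2 RNA from nasal swabs at approximately days 1, 7 and 14 among a subset". No size or selection rule is given for the subset.

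Section 10.6.2 gives two analyses. For detectability, "Detectable versus not detectable SARS-CoV-2 RNA from nasal swabs at days 7 and 14 will be compared by demographic and treatment variables", by Fisher exact tests. For the quantitative result, "continuous measures of SARS-CoV-2 RNA (on log10 scale) will be assessed for normality and tested using t-tests or Wilcoxon rank sum tests". The second sentence names no day, no change score and no covariate.

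On timing, the heading of section 6.2.9 reads "Study Day 1 (day of first study substance administration"), so Day 1 is the day dosing starts. The same section adds: "The nasal swab home kit can be completed within days 1 to 3 to accommodate shipping limitations". No section requires that swab before the first dose.

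On supply, section 6.2.8 lists "3 sets of COVID-19 Test Home Collections Kits" among the kit contents, beside the study agent, and describes an assay that determines whether RNA is present or absent. Footnote c of the schedule (section 6.1) begins "Study kit contains: Copy of informed consent, Information about the study, Instructions on study procedures" and goes on to the study agent, but lists no swab kits.

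**The concern.** Viral RNA at entry is a natural covariate for viral RNA a week or two later, and the trial plans to collect it. A two-sample t-test or Wilcoxon test on follow-up values makes no use of it, nor of the risk stratum used in the randomisation. Section 10.6.1 already allows covariate-adjusted models for the health-event outcomes, so adjustment would fit the plan's own approach.

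The sampling window adds a second problem. If the first swab is taken after dosing has begun, it may already carry part of any treatment effect, and adjusting for it could remove some of that effect. The covariate is safe only if it is measured before the first dose, so timing and analysis have to be settled together.

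The unexplained subset leaves the denominator unclear for the RNA outcome, and also for compliance with repeated testing (10.2.2.4).

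**Working it through.** The plan gives no sample size, power, standard deviation or expected rate for RNA, so there is no figure of its own to reproduce. Everything marked assumed below is illustrative.

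**1. Doses before the first swab.** Section 3: "Participants will receive either XFBD (10 g orally twice a day) for 14 days or a placebo twice a day for 14 days". That is 2 × 14 = 28 doses. The swab window is Days 1 to 3. By the end of Day 2 up to 2 × 2 = 4 doses may have been taken, and by the end of Day 3 up to 2 × 3 = 6, or 6/28 = 21% of the course.

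**2. Precision for log10 RNA.** With n per arm and outcome SD σ, the variance of the treatment difference is 2σ²/n unadjusted. Adjusted for a pre-dose value with correlation ρ, it is 2σ²(1 − ρ²)/n, ignoring the small cost of the extra model terms. The planned n is 30 per arm (section 3). Assumed: ρ of 0.3 to 0.7, two-sided alpha 0.05, 80% power. The unadjusted detectable difference is (1.960 + 0.842) × √(2/30) = 0.72 SD. Multiplying by √(1 − ρ²):

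| Assumed ρ | Variance cut (ρ²) | Equivalent sample, 1/(1 − ρ²) | Detectable difference |
|---|---|---|---|
| 0.3 | 9% | 1.10 | 0.69 SD |
| 0.5 | 25% | 1.33 | 0.63 SD |
| 0.7 | 49% | 1.96 | 0.52 SD |

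**3. Detectability.** Criterion 4.2.3 requires a positive molecular test on a specimen taken less than 96 hours before entry, so Day 1 detectability should be nearly constant. For binary measures with prevalence p1 on Day 1 and a lower p2 at follow-up, the largest possible squared correlation is p2(1 − p1) / [p1(1 − p2)]. Assume p1 = 0.95:

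- p2 = 0.2: 0.010/0.760 = 1%
- p2 = 0.5: 0.025/0.475 = 5%
- p2 = 0.8: 0.040/0.190 = 21%

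These are ceilings. They are reached only if nobody undetectable on Day 1 is detectable later. The gains in step 2 therefore do not carry over to the Fisher comparisons.

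**4. Subset or everyone.** Sections 1.3.8 and 10.2.2.7 restrict RNA to a subset. The swab row of the schedule, the kit list in 6.2.8, the Day 1, 7 and 14 procedures (6.2.9, 6.2.11, 6.2.12) and the analysis set in 10.6 carry no such restriction. Footnote c, which omits the swab kits, does not fit 6.2.8. The documents do not settle which is meant. The choice matters: by the formula in step 2, the unadjusted detectable difference is 0.72 SD at 30 per arm, and at assumed subset sizes of 20, 15 and 10 per arm it is 0.89, 1.02 and 1.25 SD. Fisher power for an assumed 80% against 50% detectable is 0.60 at 30 per arm, 0.25 at 15 and 0.13 at 10.

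**The case against.** The best defence is that this is the last-listed secondary outcome in a pilot that section 10.6 says is not powered for treatment differences, and that section 10.6.2 uses the comparisons for planning only. That stands, and it limits the severity.

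It is also fair that Day 1 is not an outcome day, so leaving it out of the detectability comparison is reasonable. For log10 RNA the plan is silent on days and covariates; it does not exclude Day 1. The assay point stands too: if the home kits return only presence or absence, there is no log10 value to adjust for.

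A reader might infer that omitting the baseline biases the treatment comparison. It does not. Randomisation protects the comparison, and the standard error of a chance imbalance, √(2/30) = 0.26 SD at 30 per arm, is already reflected in the unadjusted test. Adjustment buys precision; its absence is not an error of validity.

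A reader might also infer that swabs from all 60 participants will be collected and some then discarded, so that the subset wording should simply be deleted. The documents do not say that. They conflict, and a subset may be intended.

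**Conclusion.** The point holds in a limited form. The planned log10 RNA tests have no stated baseline or stratum adjustment, and the swab that could serve as baseline may follow up to 6 doses. The cost is precision in the continuous measure: a variance reduction forgone of about 9% to 49%, for an assumed correlation of 0.3 to 0.7 with a true pre-dose value. The documents give no correlation, so that range is an assumption. It also presumes a quantitative assay and a roughly linear relation, which many undetectable follow-up results would weaken. Little would be gained for detectability. The subset wording is a separate inconsistency to reconcile. Overall the severity is minor.

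**What to change.** - Section 6.2.9: require the first swab before the first dose, and record the time of both. A swab nevertheless taken after dosing should be flagged and not used as the baseline, with a prespecified rule for the missing covariate so that nobody is dropped.
- Section 10.6.2: compare log10 RNA at Days 7 and 14 by a linear model (ANCOVA) adjusting for the pre-dose log10 value and the risk stratum. State the value given to undetectable results. Keep the Fisher tests for detectability, and report missing swabs by arm.
- Section 6.2.8: state whether the assay returns a quantitative value, and reconcile this with the log10 outcome. If it does not, the ANCOVA change falls away.
- Sections 1.3.8 and 10.2.2.7: reconcile the subset with the schedule and its footnote c, with 6.2.8, 6.2.9, 6.2.11 and 6.2.12, and with 10.6. If a subset is meant, give its size and selection rule. If everyone is swabbed, analyse all returned swabs.

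The cost is wording, plus two recorded times per participant. Swabbing first looks practical if swabs and study agent arrive together, as 6.2.8 indicates. The downside is that some first samples may wait longer for shipping, which is the reason given for the present window.

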10.7 Unblinding

In the event that single patient unblinding is required for emergency disclosure, the sponsor investigators and medical monitor should be contacted by telephone and will make the determination should an event arise. The sponsor investigator or pharmacist will make that information available to the treating physician.

Planned Unblinding

Unblinding of all study participants will take place after the last participant has completed the study, all data have been entered into the database and cleaned for primary and secondary endpoints.

11 DATA COLLECTION AND MONITORING

11.1 *Records to Be Kept*

Electronic case report form screens will be made available to sites for data entry. Participants will be identified by the patient identification number provided upon randomization.

11.2 *Data Management*

Instructions concerning entering study data on eCRFs will be provided. Study coordinators are responsible for keying the data in a timely fashion.

Given the epidemic spread of SARS-CoV-2 and the risk for visiting personnel, the study can be monitored remotely by clinical trial monitors.

12 PARTICIPANTS

12.1 *Institutional Review Board (IRB) Review and Informed Consent*

This protocol and the informed consent document ([Appendix 1](#)) and any subsequent modifications will be reviewed and approved by the IRB or EC responsible for oversight of the study. Informed consent will be obtained from the participant through appropriate remote consenting procedures. The eIC will describe the purpose of the study, the procedures to be followed, and the risks and benefits of participation. A copy of the consent form will be provided to the participant and this fact will be documented in the participant's record.

12.2 *Participant Confidentiality*

All laboratory specimens, evaluation forms, reports, and other records that leave the site will be identified by coded number only to maintain participant confidentiality. All records will be kept locked. All computer entry and networking programs will be done with coded numbers only. Clinical information will not be released without written permission of the participant, except as necessary for monitoring by IRB/EC, the FDA, OHRP, other local, US, and international regulatory entities as part of their duties.

12.3 *Study Discontinuation*

The study may be discontinued at any time by the FDA, IRB/EC, or OHRP as part of their duties to ensure that research participants are protected, or the industry supporters.

13 PUBLICATION OF RESEARCH FINDINGS

Publication of the results of this trial will be published and submitted to [clinicaltrials.gov](#).

14 BIOHAZARD CONTAINMENT

As the transmission of SARS-CoV-2 and other droplet-borne pathogens can occur through contact with persons with active SARS-CoV-2 secretion precautions will be employed by all personnel in the clinical research setting and shipping and handling of all specimens for this study, as currently recommended by the Centers for Disease Control and Prevention and the National Institutes of Health.

All dangerous goods and materials, including diagnostic specimens and infectious substances, must be transported using packaging mandated by CFR 42 Part 72. Please refer to instructions detailed in the International Air Transport Association (IATA) Dangerous Goods Regulations.

APPENDIX III: THE SOURCE AND AUTHENTICATION OF MEDICINALS IN XUANFEI BAIDU GRANULES (XFBD)

Example English Translation for Ephedrae Herba *Full Chinese Document in Supplement Materials*

8.1.1. Ephedrae Herba (麻黃)

8.1.1.1 Resource Overview

1. Chinese Pharmacopeia Botanical Sources

The 2015 Chinese Pharmacopeia refers to three botanical sources for ephedrae herba: *Ephedra sinica* Stapf, *Ephedra intermedia* Schrenk et C. A. Mey. or *Ephedra equisetina* Bge. The grassy green stems are harvested and dried in the autumn.

2. Analysis of Botanical Sources

a. Production

Species	Growing Environment	Main Production Region	Authentic Production Region
Ephedra sinica Stapf.	Mostly Wild	Chifeng, Inner Mongolia	Inner Mongolia, Gansu
Ephedra intermedia Schrenk et C. A. Mey.	Wild	Gansu, China	
Ephedra equisetina Bge.	Wild	Xinjiang, China	

b. Confusion of Differentiating Botanical Sources

Historically, all three kinds of ephedra plants were used for medicinals. [1]. China used to be the world's largest producer of ephedrine extract so the demand for wild ephedra was overwhelming, leading to the destruction and misuse of wild resources. In the early 2000s, the chemical synthesis of ephedrine on an industrial scale was successful. Therefore, the demand for wild ephedra fell substantially. Confusion on differentiating ephedra plants has essentially disappeared, and *Ephedra sinica* Stapf. is what is available on the main medicinal market.

c. Current Resource Status and Future Trends

The resource types of ephedra are divided into two categories: wild and cultivated ephedrae herba. For wild ephedrae herba, Chifeng, Inner Mongolia produces *Ephedra sinica* Stapf with an annual output of 1,000-2,000 tons, accounting for more than 60% of the usage in China. This is followed by *Ephedra intermedia* Schrenk et C. A. Mey. produced in Gansu and *Ephedra equisetina* Bge produced in Xinjiang. The other type is cultivated *Ephedra sinica* Stapf., which is mainly produced in Lanzhou, Gansu, Ordos, and elsewhere in Inner Mongolia, and the output is not as large (see Tiandi.com <https://www.zyctd.com/zixun/202/20533.html> for information on Chinese herbal medicine and market research information). Currently, the wild resources of ephedrae herba are abundant. At one point, they were greatly reduced due to the demand to extract ephedrine. However, this burden has been alleviated with the ability to completely synthesize the compound chemically. The ephedrae herba use in traditional Chinese medicine is relatively small in comparison, thus no longer posing a threat to the wild resource. The harvest is government-regulated so the price has been reasonable since the fall of 2011. The market for ephedrae herba is very stable. A small amount of cultivated ephedrae herba has been available since the beginning of the 2000s, and these cultivators have received government permission to continue their small-scale research. At this time, the wild resources have recovered and have strong self-regeneration capabilities. The main source of ephedrae

herba will continue to be from the wild.

d. Resource Availability

Wild *Ephedra sinica* Stapf. is readily available for medicinal use. Cultivation technology is now mature so there is no risk of insufficient resource in the foreseeable future.

8.1.1.2 Quality Assurance

1. 2015 Chinese Pharmacopeia Book 1 Quality Standards and Regulations

Refer to 8.2.1.1 The raw herb shall not have less than 0.80% of ephedrine hydrochloride and pseudoephedrine hydrochloride; the decoction pieces have the same requirements.

2. Production Sites and Other Factors that Affect Quality (Mainly the Chemical Content)

a. Different Varieties

Different varieties of ephedrae herba have differing amounts of active ingredient. Jin Ling et. al [2] found that the varieties of ephedrae herba in Gansu and Inner Mongolia have different amounts of ephedrine and pseudoephedrine, which were 0.78-1.97% and 0.47-0.97% respectively

b. Different Production Region

Different production areas did not amount to any significant differences in the amounts of active ingredient. For example, Chen Kang et al. [3] showed that the ephedrine and pseudoephedrine content for the regions Inner Mongolia, Shanxi, and Ningxia were 1.30-1.56%, 1.08-1.83% and 1.30-2.16% respectively.

8.1.1.3 Selection of Variety and Production Region

1. Selection

Ephedra sinica Stapf. from Chifeng, Inner Mongolia, as the main production region, was selected for the production of Xuanfei Baidu granules (XFBD). The resource is readily available. Since its native to the region and the locals also use the same variety, the confusion of differentiating plant varieties can be avoided.

2. Quality Inspection Results

The quality inspection results of the decoction pieces of ephedrae herba can be found at 8.2.1.3 and 8.2.1.4. The quality of the decoction pieces selected for XFBD research and production meets quality assurance standards.

Figure 8-1: Ephedrae Herba Decoction Pieces Quality Inspection Results

Serial Number	Batch Number	Production Region	Appearance	Microscopic Identification
2	1910000801	Inner Mongolia	Pass	Pass
Physical and Chemical Identification	Thin-Layer Chromatography (TLC)	Moisture % cannot be greater than 9.0%	Total Ash % cannot be greater than 9.0%	Total % of Ephedrine and Pseudoephedrine cannot be less than 0.80%
Pass	Pass	7.2%	7.3%	3.25%

[1] 肖培根主编. 新编中药志 (第三卷) [M]. 北京: 化学工业出版社, 2002, 297-309.

[2] 晋玲, 张弦飞, 崔治家, 等. HPLC法测定不同产地和种属麻黄中麻黄碱与伪麻黄碱的含量[J]. 中兽医医药杂志, 2013, 32(01):43-46.

[3] 陈康, 林文津, 林励. HPCE法测定不同产地麻黄中麻黄碱和伪麻黄碱的含量[J]. 中药材, 2005, 28(8):664-665.

